**PRÉCIS**

**Study Title**

Study of Hyerkyphosis, Exercise and Function-SHEAF

**Objectives**

Our long-term goal is to develop interventions to delay functional decline and physical disability in older adults. Exercise interventions targeted at increasing function in older adults often neglect posture and spinal muscle weakness. We propose a paradigm where we can improve physical function in an exercise intervention targeted at reducing hyperkyphosis, which may reduce associated disability.

**Design and Outcomes**

We propose to conduct a randomized, controlled trial among 100 men and women aged 60 or older with hyperkyphosis to an exercise intervention that includes kyphosis-specific spinal muscle strengthening exercises compared to a non-kyphosis specific stretching exercise control. The study will be conducted in five waves, with 10 participants in the exercise intervention and 10 participants in the control group in each wave.

The experimental and control interventions will be provided in small groups meeting three sessions per week for 6 months. At baseline and 6 months after the intervention, we will measure kyphosis, physical function, spine muscle strength and density, and quality of life.

We will assess the effect of the intervention on the co-primary outcomes of kyphosis, modified PPT (PPT) and gait speed measured as change over 6 months. We will also assess the effect of the intervention on secondary outcomes of physical function and HRQOL, measured as change in Timed Up and Go, Timed Loaded Standing, Six-Minute Timed Walk, the Scoliosis

Research Society SRS-30 (self image domain only) and the PROMIS Physical Function and Global Health Index.

Furthermore, we will investigate whether changes in kyphosis, spinal muscle strength and/or density mediate the effect of the intervention on change in physical function. After the 6-month intervention, both groups will continue their usual activity and we will assess the durability of the effects of the intervention at 1-year follow-up.

### **Interventions and Duration**

Participants assigned to the intervention group will receive a kyphosis-specific spinal strengthening group exercise program for 1 hour three times per week for 6 months, followed by 6 months of usual activity. The participants assigned to the control group will receive a non-kyphosis specific stretching group program for 1 hour three times per week for 6 months, followed by 6 months of usual activity. The intervention and the control group sessions will be conducted in small groups at study intervention sites. A licensed physical therapist will teach the kyphosis-specific strengthening exercise intervention and a different physical therapist will teach the stretching intervention. Physical therapy students and/or research assistants will help ensure the safety of all participants and maintain a ratio of no more than 5 participants to 1 teacher.

### **Sample Size and Population**

One hundred subjects of men and women age 60 years and older and with kyphosis of  $\geq 40^\circ$  will be recruited for this study. In our pilot study, we observed a 2 standard deviation (SD) improvement in kyphosis of  $6^\circ$ . Allowing for improvements in the control group due to regression to the mean, loss to follow-up of 10% of participants, chance under-estimation of the SD of the change in the pilot, and attenuation of the treatment effect due to the imputation procedure, the proposed combined sample size of 100 will provide 80% power in 2-sided tests with a type-I error rate of 5% if the between-group difference in mean kyphosis improvements is at least 50% of the SD of the changes; this calculation accounts for the correlation of the pre- and post-intervention measurements (0.8 for both kyphosis and PTT scores in the pilot study), which will improve efficiency by reducing residual error in the proposed ANCOVA analysis procedure. The pilot study gives strong evidence that these conditions will be met. Similarly, we observed a 1-SD improvement of 2 points in the co-primary PPT endpoint. Thus the study will also be well powered to detect an effect on PTT scores under similarly conservative assumptions about the effect size and retention.

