## **9. STATISTICAL CONSIDERATIONS**

### **9.1 General Design Issues**

**Overview:** The primary analyses will be by treatment assignment, without regard to adherence to the intervention. Improvements in kyphosis, the Modified Physical Performance Test (PPT), and gait speed at 6 months will be co-primary endpoints. The Hochberg procedure will be used in testing the effect of treatment on these three endpoints. However, given fiscal and feasibility limitations on this

single-site study, tests of treatment effects on 5 additional physical function and HRQOL measures (Aim 2), as well as muscle strength and density (Aim 3), and all 9 comparisons at 1 year, will be regarded as secondary and analyzed without penalty for multiple comparisons, but with results clearly presented as hypothesis-generating.

In preliminary analysis, we will use t-, Wilcoxon, chi-square, and Fisher exact tests as appropriate to compare the treatment and control groups in terms of baseline age, gender, co-morbidities, vertebral fractures, physical activity and level of kyphosis. If between-group imbalances are found, sensitivity analyses will be conducted adjusting for the imbalanced covariates. However, the primary analysis will be unadjusted, to avoid inflation of type-I error and erosion of confidence due to model selection.

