## 9.2 Sample Size and Randomization

**Sample size calculation:** We calculated minimal detectable effects (MDE) with 80% power in 2-sided tests with a Bonferroni-corrected type-I error rate of 5%, in a sample of 100, allowing for within-subject correlation of the baseline and 6-month outcomes, and loss to follow-up of 20% of participants. This trial is powered to detect a difference in change in kyphosis over 6 months of 2.2 degrees (or more) between the intervention and control groups. Although the expected improvement in kyphosis is small, the hypothesis underlying this study is that preventing the expected progression of kyphosis, and improving kyphosis even a small amount, in combination with improvements in strength and conditioning, will result in meaningful improvements in physical function. In addition, the MDE for PPT and gait speed are comparable to clinically meaningful changes defined by Perera. Moreover, the MDE for kyphosis, PPT and gait are plausible in view of our uncontrolled pilot study results showing mean improvement of 6 degrees in kyphosis, 2 points in PPT and 0.05 m/s in gait speed over 3 months. Even if regression to the mean and spontaneous improvement account for almost half of the mean improvement in our pilot study, our 6 month intervention is likely to yield benefits larger than the MDE in our trial. Standard methods for ANCOVA, positing reductions in residual variance by a factor of 1-r due to adjustment for the baseline value of the outcome, were used to obtain these estimates; here r is the within-subject correlation. We used data from the pilot study to estimate r as 0.8 for kyphosis and PPT, and 0.85 for gait speed; we also used pilot data to obtain residual SD (5, 2.6, and .18 respectively).

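### The précis's 80% power for kyphosis is about 70% on its own inputs and conflicts with section 9.2, and the pilot gain in gait speed is smaller than the effect section 9.2 can detect

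*Combined protocol and SAP*

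**What the plan says.** **Précis, Sample Size and Population.** With 100 participants and a two-sided 5% test, power for kyphosis is given as 80% "if the between-group difference in mean kyphosis improvements is at least 50% of the SD of the changes". The text says that this allows for "loss to follow-up of 10% of participants" and for a pre-post correlation of 0.8 exploited by ANCOVA. It also lists regression to the mean in controls, under-estimation of the SD in the pilot, and attenuation from imputation, without giving a size for any of them.

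**Section 9.2, Sample Size and Randomization.** The same N and power are used, but with a Bonferroni-corrected 5% and "loss to follow-up of 20% of participants". The MDE for kyphosis is 2.2 degrees. No MDE is printed for PPT or gait speed, yet "the MDE for kyphosis, PPT and gait are plausible in view of our uncontrolled pilot study results", namely mean gains of 6 degrees, 2 points and 0.05 m/s over 3 months. The section then concedes that part of the pilot gain may be spurious ("Even if regression to the mean and spontaneous improvement account for almost half of the mean improvement in our pilot study") and still concludes, without excluding any of the three endpoints, that "our 6 month intervention is likely to yield benefits larger than the MDE in our trial". On inputs it says "we also used pilot data to obtain residual SD (5, 2.6, and .18 respectively"), with r of 0.8, 0.8 and 0.85 and a residual-variance factor of 1 − r².

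**Section 9.1.** Kyphosis, PPT and gait speed are co-primary, and the Hochberg procedure "will be used in testing the effect of treatment on these three endpoints".

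**The concern.** The précis expresses its effect in units of the SD of change. Change scores already carry most of the benefit of a high pre-post correlation, so ANCOVA adds little on that scale, and 45 per arm looks too few for 80% power at half an SD. The two sections also give one co-primary endpoint two detectable effects, under different loss rates and different error rates.

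For gait speed, section 9.2 defends an MDE that it never prints by pointing to a pilot gain of 0.05 m/s. If the MDE is larger than that, the pilot cannot support the defence, least of all after the discount that the section itself applies. A null gait result would then be read against a stated expectation that the plan's own inputs do not bear out.

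**Working it through.** **Section 9.2 first: does 2.2 degrees reproduce?**

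Inputs: 100 randomised 1:1, 20% loss, so n = 40 per arm; three co-primaries, so α = 0.05/3; SDs 5, 2.6 and 0.18; r = 0.8, 0.8 and 0.85.

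MDE = (z₁₋α/₂ + z₀.₈) × SD × √(1 − r²) × √(2/n), with z-sum 2.394 + 0.842 = 3.236 and √(2/40) = 0.2236.

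- Kyphosis: 3.236 × 5 × 0.600 × 0.2236 = **2.17 degrees**. The stated 2.2 reproduces.
- PPT: 3.236 × 2.6 × 0.600 × 0.2236 = **1.13 points**.
- Gait: 3.236 × 0.18 × 0.527 × 0.2236 = **0.069 m/s**.

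The kyphosis figure reproduces only if 5 is the outcome SD *before* baseline adjustment. If 5, 2.6 and 0.18 were already residual, the MDEs would be 3.6 degrees for kyphosis and 0.130 m/s for gait.

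**Précis power.**

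Inputs: n = 45 per arm after 10% loss, two-sided α = 0.05, difference = 0.5 SD of change, r = 0.8.

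Let k be the 6-month SD divided by the baseline SD. The ratio of ANCOVA residual variance to change-score variance is k²(1 − r²)/(1 + k² − 2rk). With k = 1 this is 0.36/0.40 = 0.90, which equals (1 + r)/2.

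- Standardised difference: 0.5/√0.90 = 0.527. Power with 45 per arm: **70.5%** (69.6% with the t distribution).
- No dropout (50 per arm): 75.0%. At the pilot's own 16% loss (42 per arm): 68%.
- For 80% power: 2 × 0.90 × (1.960 + 0.842)²/0.25 = 56.5, so 57 analysed per arm; or 0.56 SD of change with 45 per arm.
- Applying 1 − r² to the SD of change counts the correlation twice and gives 97.7%. A one-sided 5% test gives 80.4%, but the text says two-sided.

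| k | variance ratio | power, 45 per arm |
|---|---|---|
| 0.80 | 0.64 | 84% |
| 0.85 | 0.72 | 80% |
| 1.00 | 0.90 | 70.5% |
| 1.25 | 1.00 | 66% |

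**Précis against section 9.2.** Half an SD of change is 1.5 degrees with the pilot SD of change of 3 (Table 1), or 1.58 degrees with SD 5 and r = 0.8 (5 × √0.4 = 3.16). Section 9.2's 2.2 degrees is 0.70 to 0.73 SD of change. Under section 9.2's settings, power at 1.5 to 1.58 degrees is 44% to 48%.

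**Gait speed against the pilot.** The MDE is 0.069 m/s at α = 0.05/3, 0.059 at α = 0.05, and 0.053 at α = 0.05 with no loss. All three exceed the full pilot gain of 0.05.

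Power with 40 per arm (residual SD 0.18 × 0.527 = 0.0948):

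| true gait effect (m/s) | α = 0.05/3 | α = 0.05 |
|---|---|---|
| 0.0275 (55% of the pilot gain, one reading of losing almost half) | 14% | 25% |
| 0.05 | 49% | 65% |
| 0.08 | 92% | not needed |

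Hochberg tests gait at 0.05 when the other two endpoints are significant. A simulation of the planned procedure (400,000 runs, correlation between endpoints 0 to 0.5) gives 64% to 66% power at 0.05 m/s when kyphosis and PPT have 55% to 100% of their pilot effects, and 49% when both are null.

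Share of the pilot gain that can be spurious before the MDE is missed:

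- Kyphosis: 1 − 2.17/6 = 64%.
- PPT: 1 − 1.13/2 = 44%. A discount of 45% to 50% leaves 1.0 to 1.1 points against 1.13.
- Gait: none; 0.0686/0.05 = 137%.

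**The case against.** **The 70% rests on an assumption that the plan does not state.** No variance ratio is given, and the 66% to 84% range includes 80%. Table 1's change SDs are rounded: if 5 is read as the *baseline* SD, k = 0.8 gives a change SD of 3.00 and power of 84%. This stands in part: 70% is a central value under a named assumption. But section 9.2 applies 1 − r² to 5 as the *outcome* SD. On that reading k = 0.85 implies a baseline SD of 5.88 and a change SD of 3.54, and k = 0.8 implies 3.75, both further from Table 1's 3 than the 3.16 under equal variances. Taking section 9.2's residual SD (5 × 0.6 = 3.0) with the pilot change SD of 3 gives a variance ratio of 1.0 and 66% power, with no ratio assumed separately.

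**The précis cannot be fully rebuilt.** True, since several allowances have no size. Added to the quantified inputs they could only lower power.

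**Kyphosis is well powered in practice.** This stands. At 3 degrees, half the pilot gain, power is 98% even at the Bonferroni level.

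**Gait is a matter of plausibility.** No printed figure is wrong. A 95% interval around the pilot mean (0.05 ± 0.10, 21 completers) runs from about 0.004 to 0.096 m/s and includes 0.069. The trial offers 72 sessions against 24 in the pilot, section 2.2 cites 0.08 m/s for a different, lower-extremity programme, and section 9.2 also calls the MDE comparable to clinically meaningful change. All of this allows a larger gait effect. None of it supports the statement that benefits would exceed the MDE after almost half of the pilot gain is removed, and a meaningful-change threshold says nothing about the effect to expect.

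**The SD label is clerical.** Agreed; no printed result changes.

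**Conclusion.** The concern holds.

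- The précis's 80% does not follow from its quantified inputs. Under equal variances power is about 70%; it reaches 80% only if the 6-month SD is about 0.85 of the baseline SD or less, which the plan nowhere states.
- The conflict with section 9.2 needs no variance assumption: the loss rate and error rate differ, and the detectable effects are roughly 1.5 against 2.2 degrees.
- The assurance that benefits will exceed the MDE is sound for kyphosis, borderline for PPT and unsupported by the pilot for gait speed. This takes section 9.2's SDs as unadjusted outcome SDs, the only reading that reproduces 2.2 degrees; the other reading makes the gait gap wider.

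The sample size, the 2.2 degrees and the analysis are not in dispute. The point should be fixed because it concerns stated power and expectations for co-primary endpoints.

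**What to change.** 1. In the précis, replace the kyphosis calculation with section 9.2's (20% loss, corrected level, MDE 2.2 degrees). If the précis calculation is kept, restate its power as about 70% and name the equal-variance assumption.
2. In section 9.2, print the MDEs for PPT (1.13 points) and gait speed (0.069 m/s).
3. Limit the statement about exceeding the MDE to kyphosis, and say that PPT is borderline after the discount.
4. State gait-speed power at 0.05 m/s: about 49% at the Bonferroni level and about 65% under Hochberg when kyphosis and PPT are significant.
5. Relabel 5, 2.6 and 0.18 as outcome SDs before baseline adjustment.

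The cost is protocol wording, and some stated figures become less favourable. No participants are added and the analysis does not change.

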## **1. STUDY OBJECTIVES**

### **1.1 Primary Objective**

We propose 3 specific aims in a randomized controlled trial comparing a 6-month high-intensity kyphosis-specific spinal strengthening exercise intervention to a control stretching intervention in community-dwelling adults 60 years and older with hyperkyphosis.

The exercise intervention will improve hyperkyphosis, as measured by Cobb angle from lateral spine radiographs. The exercise intervention will also improve physical function, as measured by the Modified Physical Performance Test, gait speed, timed loaded standing and spinal extensor muscle strength.

**Specific Aim 1: To determine if the exercise intervention improves kyphosis, the Modified Physical Performance Test (PPT) and gait speed in person with kyphosis**

**Hypothesis 1:** We hypothesize that the co-primary outcomes of kyphosis, measured as Cobb angle using lateral spine radiographs, and physical function, measured as the Modified Physical Performance Test and gait speed, will improve after the 6-month intervention.

### **1.2 Secondary Objectives**

**Specific Aim 2:** Determine if the exercise intervention improves secondary measures of physical function, and health-related quality of life (HRQoL) .

**Hypothesis 2:** We hypothesize that secondary measures of physical function, including Timed Up and Go, Timed Loaded Standing, and HRQOL, measured as the Scoliosis Research Society SRS-30 (self image domain) and PROMIS Physical Function and Global Health Index, will improve after the 6-month intervention.

**Specific Aim 3:** Determine if the exercise intervention improves spinal muscle strength and/or spinal muscle density and if changes in spinal extensor muscle strength and/or density mediate the effects of change in kyphosis on physical function.

**Hypothesis 3:** We hypothesize that spinal muscle strength, measured with a Biodex computerized dynamometer, and spinal muscle density, measured with quantitative computed tomography, will improve after the

6-month intervention. We hypothesize that the intervention will have direct effects on function, as well as indirect effects on function via kyphosis, muscle strength, and density; we also hypothesize an indirect effect of the intervention on kyphosis via strength and density.

## **2. BACKGROUND AND RATIONALE**

### **2.1 Background on Condition, Disease, or Other Primary Study Focus**

**Hyperkyphosis is a highly prevalent condition among elderly persons.** While a small amount of anterior curvature of the thoracic spine (kyphosis) is normal due to the shape of the vertebral bodies and intervertebral discs, a thoracic curvature between T4 and T12 that is greater than 40 degrees is defined as hyperkyphosis. Persons with hyperkyphosis have a global misalignment of the spine, measured as a plumb line from C7 to S1 falling in front of the sacral promontory. Several methods quantify kyphosis, including lateral radiographic Cobb angle of kyphosis (the gold standard), and clinical measures including Debrunner kyphometer, supine block method for forward head alignment, occiput to wall distance, electric inclinometer, and flexicurve kyphosis index. There is a strong correlation between radiographic Cobb angle and Debrunner kyphometer measures of kyphosis and these are often used interchangeably. Reports of prevalence of hyperkyphosis in older adults vary from approximately 20% to 40% among men and women. It is estimated that kyphosis angle is 6 - 11% higher per decade of life among women age 55-80 years, and kyphosis increases 7 degrees over 15 years among women in the longitudinal Study of Osteoporotic Fractures.

**Hyperkyphosis is not synonymous with spinal osteoporosis.** It is often assumed that hyperkyphosis is caused solely by osteoporosis and vertebral fractures, but only a third of individuals with severe hyperkyphosis have radiographic vertebral fractures. In fact, recent evidence suggests that impairments in spinal muscle composition, strength, mobility and alignment are important determinants of the degree of kyphosis. Higher multisegmental spinal loads and trunk muscle forces are present in the hyperkyphotic vs. normal spine, and improving the biomechanics of spinal load and muscle force distribution could potentially ameliorate the detrimental effects of kyphosis and slow kyphosis progression. To date, small studies have demonstrated that kyphosis-related impairments can be targeted with exercise, but none have established whether reducing these impairments prevents kyphosis progression, or leads to improvement in physical function.

- ***Spinal muscle weakness.*** Spinal extensor muscle strength is an important independent determinant of degree of kyphosis in older adults. Recent studies demonstrate that spinal extensor muscle strength can be increased with targeted strengthening, however the effects on kyphosis have been inconsistent. The only large randomized exercise trial did not improve Cobb angle or Debrunner kyphometer kyphosis. High-intensity strengthening rather than low-intensity or yoga-type exercise may be necessary to reduce the Cobb angle or Debrunner kyphosis.
- ***Spinal muscle fat infiltration.*** We examined fat infiltration in the spinal extensor

muscles on quantitative computed tomography (CT) among healthy community-dwelling older men and women and found lower spinal muscle density (a proxy measure of fat infiltration) among older adults with hyperkyphosis. Furthermore, lower spinal muscle density is a known predictor of impaired physical function in older adults, suggesting that improved muscle quality is a possible mechanism for improving physical function that we will investigate in our study.

- **Spinal mobility.** Decreased spinal mobility interferes with the ability to stand erect and maintain optimal postural alignment. Schenkman, et al. determined that hyperkyphosis results in the loss of combined spinal extension and rotation mobility which is highly correlated with impaired physical performance. Furthermore, short pectoral and hip flexor muscles are linked to severe hyperkyphosis, although it is not known whether the short muscles pull the shoulders and hips anteriorly, increasing kyphosis, or whether the kyphosis results in shorter anterior musculature.
- **Spinal alignment.** Hyperkyphosis may be partially attributed to poor postural habits. Postural taping produced immediate reduction in kyphosis, although it was not sustained without mechanical support from the tape. Specific postural training, combined with strengthening, might be most effective.

Exercise trials to reduce hyperkyphosis are limited. Several randomized studies of physical activity interventions have demonstrated improvement in clinical measures of kyphosis, but none has demonstrated a link between improvement in kyphosis and change in physical function. None of these trials used high intensity spinal extensor strengthening to reduce hyperkyphosis while targeting all known musculoskeletal impairments associated with hyperkyphosis.

## 2.2 Study Rationale

**2.3 Exercise trials to improve physical function in the elderly are feasible and effective.** There is strong evidence from 121 randomized controlled trials reviewed in a Cochrane Collaboration meta-analysis that people aged 60 years and older who perform resistance exercises become stronger (standardized mean difference (SMD)=0.84, 95% CI 0.67 to 1.00) and improve their physical function (SMD=0.14, 95% CI 0.05 to 0.22). The majority of these resistance exercise programs target lower extremity muscle groups, and none of these trials targeted the spinal muscles or hyperkyphosis. Lower extremity resistance exercise is effective in improving walking speed (SMD=0.08 m/s, 95% CI 0.04 to 0.12) and rising from a chair (SMD -0.94, 95% CI -1.49 to -0.38). In subgroup analyses, when high intensity resistance exercise was compared to low intensity training, both are effective; however, high-intensity training has a larger effect on strength than low intensity training (SMD=0.48, 95% CI 0.03 to 0.93; test for subgroup differences, p=0.07). Even individuals in their 80's benefit from high-intensity resistance exercise and are capable of improving strength and physical

function. Among 100 frail nursing home residents, mean age  $87 \pm 0.6$  years, lower extremity high-intensity resistance exercise 3 times a week for 10 weeks increased lower extremity strength  $113 \pm 3.8\%$ , gait speed  $28 \pm 3.8\%$  and stair climbing  $28 \pm 6.6\%$ . Furthermore, serious adverse effects from high intensity resistance exercise are rare when used appropriately in older adult populations. While musculoskeletal complaints such as joint pain and muscle soreness were reported in many studies, no serious events related to the exercise interventions were reported in the meta-analysis of 121 trials of progressive resistance strength training in older adults.

Unfortunately, these trials did not focus on older adults with hyperkyphosis, and it is not clear if the findings can be generalized to this group. Furthermore, these trials did not target spinal muscle strength that can be amenable to intervention. High-intensity spinal extensor strengthening exercise has not been well investigated in older adults with hyperkyphosis. In contrast, in an uncontrolled trial we demonstrated that a high-intensity spinal extensor strengthening exercise intervention improved spinal extensor muscle strength, reduced kyphosis, and improved physical function for elders with hyperkyphosis. The benefit of reducing hyperkyphosis on physical function has not been demonstrated in a full-scale randomized controlled trial. Additionally, no clinical trials have investigated whether exercise that improves kyphosis, spinal muscle strength and/or spinal muscle density predicts improved physical function.

In [name] pilot trial, after 12-weeks of training, we observed a  $6^\circ$  decrease in Debrunner kyphosis, an 11% improvement from baseline and exceeding the amount of progression in kyphosis typically observed over a decade in older females. In addition to improvement in kyphosis, physical function improved 2 points ( $p < 0.001$ ) on the Modified Physical Performance Test, a 9-item composite test of physical performance, and 1.4 seconds ( $p < 0.001$ ) on the jug test ( $p < 0.001$ ), a timed lifting test (table1).[21] Improved kyphosis and gains in physical function were maintained 1 year after the participants completed the intervention. [name] was responsible for all phases of the study, including conceptualization, design, development of forms, recruitment, implementation, data management, and analysis and presentation of results.

